2.1 Overall study design

This is a multinational, multicenter, retrospective, observational study of antidepressant drug utilisation among an inception cohort of patients under specialists (psychiatrists) care who are prescribed Seroquel XR for treatment of major depressive episodes associated with MDD following launch of the indication in each country. The study will be conducted in 5 European countries: Germany, Italy, Romania, Spain, and Sweden to ensure geographic representation across European member states. The sponsor may include alternate EU country(ies) based upon limited use of Seroquel XR for MDD in the countries listed and whose selection will maintain geographic representation among EU countries.

The inception cohort is defined as patients initiating Seroquel XR (as add-on therapy or as monotherapy) during a 9 month period corresponding to 3 to 12 months following the launch of the product in each country for the MDD indication. In the period immediately after launch, physicians may not be aware of the approval of Seroquel XR for add-on treatment for MDD. Therefore, patients treated with Seroquel XR within the 3 months after launch will not be included in the inception cohort because they are not likely to be representative of patients

[figure not shown]
treated in subsequent periods. A drug utilisation questionnaire will be used to collect study data. Data collection will be initiated following a study-defined index date, approximately 12 months after product launch. All study sites within a country will be assigned the same index date and will not be contacted prior to the index date.* Initiation of site-specific activities for selection of patient records meeting study selection criteria will commence on or following the index date. Data on drug utilisation will be censored on the index date. This approach will ensure that study procedures do not influence prescribing practices.

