3.3.1 Inclusion Criteria for Patients

1. Provision of informed consent before initiation of any collection of questionnaire data.
2. Female and male aged 18 years and over.
3. Documented clinical diagnosis of Major Depressive Disorder, Single Episode, or Recurrent.
4. Initiation of Seroquel XR for treatment of MDD during the period defining the inception cohort, i.e. from 3 months after launch until the index date.

The prescription of the medicinal product is clearly separated from the decision to include the patients in the study.

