4.2.2 Key Variables - Psychiatrists, Subjects, and Drug Utilisation

The drug utilisation questionnaire is constructed to collect key variables on characteristics of physicians, patients and the drugs utilised in the medical management of depressive episodes in MDD where the treatment regimen includes Seroquel XR.

Information on participating psychiatrists will include:

- location of practice (i.e., country, region, and city or town)
- age
- gender
- years in practice
- practice setting (i.e., mental health clinic, university-affiliated hospital, community hospital, private practice office, other)
- proportion of patient volume in hospital versus non-hospital

- approximate proportion of patients with a diagnosis of MDD in their practice

Information on patients will include:

- demographics (date of birth, gender, race)
- source and reason for referral of the patient
- general medical and psychiatric history (i.e., date of first depressive episode, start date of most recent depressive episode, month and year of diagnosis of MDD, total number of depressive episodes over lifetime, number of depressive episodes during the 12 months up to the latest consultation, presence of psychotic symptoms in the past, psychiatric co-morbidities (anxiety disorders, substance use, other Axis I, or other Axis II disorder), other medical co-morbidities (i.e., hypertension, obesity, diabetes, other cardiovascular), ever been hospitalised for a psychiatric condition, ever hospitalised for MDD, and whether hospitalised during most recent depressive episode)

Information on drug utilisation will include, where recorded:

- treatment history including details on current and past drug treatments for MDD (including Seroquel XR) within the past 12 months (historical information based on patient reported drug use may be required if physician has been treating the patient for < 12 months), dose/duration of drugs used to treat MDD (including any drug treatments for MDD noted in the patient's medical record that were prescribed by other physicians), including changes in medication, date of initiation/end for each drug; and whether drug treatments for MDD prescribed with Seroquel XR were still prescribed on the index date; for Seroquel XR treatment details include frequency of prescriptions by dose, prescribed days supply by dose, initial dose, usual (modal) dose, maximum dose
- diagnosis for which Seroquel XR is being prescribed

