9.2 Patient's demographic data and psychiatric history

Summary statistics will be provided by country and overall for patient's demographics data including age, gender, and race, and for patient's medical history including years since first depressive episode, year of MDD diagnosis, number of depressed episodes over lifetime, number of depressive episodes during the 12 months up to the latest consultation, presence of psychotic symptoms in the past, presence of psychotic symptoms at start of Seroquel XR

treatment, psychiatric co-morbidities (anxiety disorders, substance use, other Axis I, or other Axis II disorder), other medical co-morbidity (hypertension, obesity, diabetes, other cardiovascular disorder), ever been hospitalised for a psychiatric condition), as well as for the number of visits to the psychiatrist during the timeframe that Seroquel XR has been prescribed.

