
If you have specified a height for this patient, has it been:

- Measured?
- Estimated?
- Not specified?

What was the patient’s weight at the visit closest to *date 1 (date 1 = 9 months prior to [INDEX DATE])*

__ kg
 Not specified?

Date that weight was:

- measured?
- reported by patient ?
- not specified?

__ / __ / __
day / mo / year

What is the race of this patient?

- White
- Black
- Asian
- Other (including native people or mixed races) – please specify _____
- Not specified

Referral Pathways

When did the investigator see this patient for the first time?

__ / ____ (month / year)

mo / year

Who referred this patient to the investigator?

Please select one answer only

- Primary care physician
- Another psychiatrist (in-patient)
- Another psychiatrist (out-patient)
- Law enforcement
- Family member
- Accident & emergency
- Social services
- Self-referral
- Other – please specify _____

Why was this patient referred to the investigator?

Please select all that apply

- Specific need for psychiatric care
- Access to specific treatments
- Severity of MDD
- Concomitant disorders / complexity of psychiatric state
- Other – please specify _____

Medical/Psychiatric History

In the table below, please record if, according to the medical record, the patient has ever reported/experienced any of the following concomitant disorders? *Please select all that apply*
 Has the patient received **drug treatment** (in the past or current) for any of these conditions?

Please select all that apply

	Ever Experienced	If experienced, is the condition past /current Circle all that apply?	Received Drug treatment (in the past)	Receiving Drug treatment (currently)
Anxiety disorder(s)	Yes / No / Unknown	Past / Current	Yes / No / Unknown	Yes / No / Unknown
Alcohol abuse	Yes / No / Unknown	Past / Current	Yes / No / Unknown	Yes / No / Unknown
Nicotine use	Yes / No / Unknown	Past / Current	Yes / No / Unknown	Yes / No / Unknown
Illicit substance abuse	Yes / No / Unknown	Past / Current	Yes / No / Unknown	Yes / No / Unknown
Other Axis 1	Yes / No / Unknown Please specify 1) _____ 2) _____ 3) _____	Past / Current Past / Current Past / Current	Yes / No / Unknown Yes / No / Unknown Yes / No / Unknown	Yes / No / Unknown Yes / No / Unknown Yes / No / Unknown

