 Yes  No  Unknown	 Yes  No  Unknown

MDD Treatment

This section is dedicated to recording **drug treatments** received by this patient for his / her MDD in the **12 months up to [INDEX DATE]**.

In the table below, please list **ALL drug treatments for MDD** that started and ended before the initiation of Seroquel XR received by the patient in the 12 months up to [INDEX DATE]. **Please include any drug treatments for MDD noted in the patient's medical record that were prescribed either by the investigator or by other physicians.** Also, for each drug treatment, please specify information on start and end date and dosing. Please record **all changes in dose** as separate line entries.

(1) Specific drug name (generic or brand names)	(2) Start date (day/mth/year) Check for "on demand" or prn use	(3) End Date (day/mth/year)	(4) Dose (specify Unit)
	-- / / --  prn	-- / / --	_____
	-- / / --  prn	-- / / --	_____
	-- / / --  prn	-- / / --	_____
	-- / / --  prn	-- / / --	_____
	-- / / --  prn	-- / / --	_____
	-- / / --  prn	-- / / --	_____

In the table below, please list **ALL drug treatments for MDD** that were **prescribed concurrently with Seroquel XR** (including Seroquel XR) received by the patient in the 12 months up to *[INDEX DATE]*. **Please include any drug treatments for MDD noted in the patient’s medical record that were prescribed either by the investigator or by other physicians.** Also, for each drug treatment, please specify information on start and end date (if applicable), dosing and dates of dose changes.

For Seroquel XR prescriptions, please record all changes in dose as separate line entries using columns (1) – (4).

Instructions: Please answer these questions for ALL drug treatments for MDD that were prescribed by the investigator or other physicians concurrently with Seroquel XR For Seroquel XR, please record all changes in dose as separate line entries
				
Instructions: Please answer these questions only for drug treatments for MDD that were prescribed by the investigator or other physicians concurrently with Seroquel XR
		

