(1) Specific drug name (generic or brand names)	(2) Start date (day/mth/year) Check for “on demand” or prn use)	(3) End Date (day/mth/year)	(4) Dose (specify Unit)	(5) Did the dose change at initiation of Seroquel XR?	(6) Most recent dose prior to [INDEX DATE] (if different than at initiation)	(7) Date of most recent dose change (day/mth/year)
	___/___/___  prn	___/___/___  Still prescribed at [INDEX DATE]	_____	 Increase  Decrease  Remained the same  Not applicable	_____  Not applicable	___/___/___  Not applicable
	___/___/___  prn	___/___/___  Still prescribed at [INDEX DATE]	_____	 Increase  Decrease  Remained the same  Not applicable	_____  Not applicable	___/___/___  Not applicable
	___/___/___  prn	___/___/___  Still prescribed at [INDEX DATE]	_____	 Increase  Decrease  Remained the same  Not applicable	_____  Not applicable	___/___/___  Not applicable
	___/___/___  prn	___/___/___  Still prescribed at [INDEX DATE]	_____	 Increase  Decrease  Remained the same  Not applicable	_____  Not applicable	___/___/___  Not applicable

Seroquel XR Treatment

Was the patient experiencing psychotic symptoms at initiation of Seroquel XR?

- Yes
- No
- Unknown

Which disorder was Seroquel XR prescribed for?

Please select all that apply

- MDD
- Schizophrenia
- Bipolar disorder
- Other – please specify _____

How many times has the investigator seen this patient since initiation of Seroquel XR?

__ visits

What is your estimate of patient adherence to the prescribed treatment regimen that included Seroquel XR for depression?

___ % of time adherent to prescribed dose(s) (range: 0 – 100%)

(Investigator assessment)

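### Prior MDD drug history is counted back from the index date, so the look-back before Seroquel XR is 3 to 12 months depending on start date; the episode and visit items are also poorly anchored

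*Protocol*

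**What the plan says.** Protocol section 2.1 defines the inception cohort as patients who start Seroquel XR "during a 9 month period corresponding to 3 to 12 months following the launch of the product in each country". Section 3.3.1 admits those who start "from 3 months after launch until the index date", and section 2.1 places the index date "approximately 12 months after product launch". The patient form in Appendix B agrees with this: "date 1 = 9 months prior to [INDEX DATE"].

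Three items use windows that matter here.

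- **Earlier MDD drugs** (Appendix B, MDD Treatment). The first table asks for all drugs "that started and ended before the initiation of Seroquel XR received by the patient in the 12 months up to [INDEX DATE"]. Section 4.2.2 mentions a 12-month treatment history but does not say from which date it is counted.
- **Depressive episodes** (sections 4.2.2 and 9.2, and Appendix B). The item is the "number of depressive episodes during the 12 months up to the latest consultation".
- **Visits**. Appendix B asks "How many times has the investigator seen this patient since initiation of Seroquel XR", with no end date. Section 9.2 plans to report the "number of visits to the psychiatrist during the timeframe that Seroquel XR has been prescribed".

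**The concern.** In an inception cohort the natural anchor for history is the day treatment starts. Here the window for ended treatments closes at a date common to the whole country, while initiation varies by up to 9 months. Two patients with identical histories can give different records only because one started soon after the cohort opened and the other just before the index date. The early starter will tend to look less pre-treated.

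Section 9 reports prescribing and drug utilisation by country so that countries can be compared. If uptake after launch follows a different course in two countries, part of any difference in recorded prior treatment would come from the form. Analysis cannot recover a drug that was never abstracted.

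The episode count raises a related problem: it is summarised as history but can include months on Seroquel XR. The visits question collects a different quantity from the one section 9.2 intends to report.

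**Working it through.** **Inputs.** Cohort opens at month 3 after launch (sections 2.1 and 3.3.1). Index date is at about month 12 (section 2.1). The drug-history window is 12 months back from index (Appendix B).

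**The plan's own figure.** Length of the inception window = 12 − 3 = 9 months. This matches the 9 months stated in section 2.1 and the definition of date 1 in Appendix B.

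**Look-back before initiation.** For a start at month m after launch, time from start to index is 12 − m. The part of the 12-month window that lies before initiation is 12 − (12 − m) = m months.

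| Start month | Start to index | Look-back before initiation | Reach back from index if 12 months before initiation were required |
|---|---|---|---|
| 3 | 9 | 3 | 21 |
| 6 | 6 | 6 | 18 |
| 9 | 3 | 9 | 15 |
| 12 | 0 | 12 | 12 |

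**Under even uptake (assumed).** Mean look-back = (3 + 12)/2 = 7.5 months. Share with less than 6 months = (6 − 3)/9 = 33%. Share with less than 9 months = (9 − 3)/9 = 67%.

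**Which ended drugs are lost.** A drug that ended x months before initiation is inside the window only if m ≥ x. Under even uptake the captured share is (12 − x)/9 for x from 3 to 12:

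- x = 3 or less: 100%
- x = 6: 6/9 = 67%
- x = 9: 3/9 = 33%

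If uptake instead rises linearly from zero at month 3, the captured share for x = 6 is 1 − (3/9)² = 89%. The protocol does not give the uptake curve or the distribution of drug end dates, so an overall loss cannot be calculated.

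**Sensitivity to the index date.** With the cohort still opening at month 3, the shortest look-back is 12 − (11 − 3) = 4 months for an index date at month 11, and 12 − (13 − 3) = 2 months at month 13.

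**Episodes.** If the latest consultation falls on the index date, the part of the 12-month window after initiation is 12 − m months. That is 9/12 = 75% for a month-3 starter, 0% for a month-12 starter, and 4.5/12 = 37.5% on average under even uptake. If the latest consultation is later than index, the share after initiation grows, because the item has no cap.

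**Visits.** The form counts from initiation with no end; section 9.2 counts only while the drug was prescribed. The two agree only if the patient had no visits after Seroquel XR was stopped.

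**The case against.** The strongest reply is that little of the planned output depends on the truncated table. Sections 9.3 and 9.4 name no count of prior treatments, and most of section 9.4 concerns drugs that overlap with Seroquel XR. Those go into a separate table with their own start dates, so an antidepressant to which Seroquel XR was added is not lost. Several central items are anchored on initiation: psychotic symptoms at the start, the Clinical Global Impression, and response to the most recent prior antidepressant, which has no 12-month limit. No statistical comparison is planned. All of this stands, and it confines the harm to the description of ended treatments.

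It is also true that drug dates are recorded, so the truncation is known for each patient and everyone could be cut back to a common 3 months before initiation. That would remove the artificial country difference, but only by discarding most of the history collected.

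A reader might infer more than the protocol supports in four ways:

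- **That both objectives are undermined.** They are not. The points above leave most patient characteristics and the Seroquel XR utilisation data intact.
- **That 11% to 33% of prior-treatment data are missed.** Those figures apply only to a drug that ended exactly 6 months before initiation, under the two uptake shapes shown.
- **That the weight item shows the same fault.** Weight is taken at the visit closest to date 1, which is usually before initiation. Its date is recorded, and it is not among the outputs in section 9.2.
- **That visits after the index date are meant to be counted.** Section 4.2.2 lists visits under drug utilisation, and section 2.1 censors drug-utilisation data at index. What remains is that the form has no end at stopping and does not repeat the cap.

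**Conclusion.** The point holds in limited form. The look-back for ended MDD treatments varies from 3 to 12 months by calendar start date. It averages 7.5 months if starts are evenly spread, and its minimum moves to 2 or 4 months if the index date falls a month late or early. It affects only drugs that ended more than 3 months before initiation (index at month 12), and its overall size is unknown. The figures also assume that all patients are true initiators, as section 3.3.1 requires.

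The 12-month episode count mixes time before and after initiation and has no cap at index. The visits question does not collect the quantity that section 9.2 reports. No test is invalidated, but the missing drug history cannot be restored at analysis, so the wording should be changed before data are abstracted.

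**What to change.** Change three items in Appendix B and align sections 4.2.2 and 9.2 with them:

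1. Prior MDD drugs: those received in the 12 months before the first Seroquel XR prescription.
2. Depressive episodes: those in the 12 months before initiation of Seroquel XR.
3. Visits: from initiation to the earlier of the last Seroquel XR day and the index date.

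The index date then serves only as the end of follow-up. Sections 4.1.2 and 4.2.2 already allow the questionnaire to be revised after the pilot, and section 4.1.3 places translation after validation, so the change fits the planned sequence.

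The cost is up to 9 more months of chart review for the earliest starters, reaching as far as 21 months before index. There will also be somewhat more reliance on patient-reported history, which section 4.2.2 already foresees for patients whom the physician has treated for less than 12 months.

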9.3 Seroquel XR utilisation

At the time of initiation of Seroquel XR, the diagnosis for which Seroquel XR was prescribed, whether the patient was experiencing psychotic symptoms, Clinical Global Impression, the initial daily dose of Seroquel XR prescribed and any concomitant antidepressant drug(s) and dose(s) prescribed will be summarized descriptively by country and overall.

The last prescribed daily dose prior to the index date, the maximum daily dose prescribed, modal daily dose, and the duration for each dose of Seroquel XR as prescribed will be summarized descriptively by country and overall.

Doses described above will be summarized in two ways.

- As continuous variable: the following will be calculated: number mean, mode, median, minimum, maximum, and standard deviation
- As a categorical variable: number and % of patients will be provided for each of the following dose levels: 50 mg, 100 mg, 150 mg, 300 mg and other.

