9.4 Other drug utilisation for MDD

The following will be summarized for treatments other than Seroquel XR for MDD the daily dose at the first initiation, whether a dose change accompanied initiation of Seroquel XR, latest dose following Seroquel XR initiation, interval from initiation of Seroquel XR to latest dose change and whether the prescription was continuing on the index date.

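### Section 9.3 promises every concomitant antidepressant at Seroquel XR initiation, but the form collects only drugs given for MDD, so antidepressant co-use can be under-counted

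*Protocol*

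**What the plan says.** Three places in the protocol set what is collected on other drugs, and all three limit it by indication.

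- Section 4.2.2 lists, among the key variables, "treatment history including details on current and past drug treatments for MDD (including Seroquel XR) within the past 12 months".
- The MDD Treatment section of Appendix B opens by restricting itself to drugs "received by this patient for his / her MDD in the" 12 months up to the index date.
- Its concurrent-drug table instructs: "Please answer these questions for ALL drug treatments for MDD that were prescribed by the investigator or other physicians concurrently with Seroquel XR". This table holds the drug name, dates, dose and dose changes.

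Treatment of other conditions appears only in the comorbidity grid of Appendix B (Medical/Psychiatric History). The grid asks whether the patient has had drug treatment "for any of these conditions", which include anxiety, other Axis 1 and other Axis 2 disorders. The answers are Yes, No or Unknown, for past and for current treatment. No drug name, dose or date is asked.

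The analysis section is not uniform. Section 9.4 carries the limit: "The following will be summarized for treatments other than Seroquel XR for MDD". Section 9.3 does not. For the time of initiation it says that "any concomitant antidepressant drug(s) and dose(s) prescribed will be summarized descriptively by country and overall".

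Section 2.1 defines the cohort as "patients initiating Seroquel XR (as add-on therapy or as monotherapy) during a 9 month period". The form has no item for add-on or monotherapy status, and Section 9 sets no rule for deriving it.

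**The concern.** The form is narrower than the output it must feed. In a patient with MDD and an anxiety disorder, an antidepressant attributed to the anxiety fits the grid, where it leaves a tick, and does not clearly belong in the drug table, where it would leave a name and a dose. Section 9.3 needs the name and the dose.

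The person who must decide is usually not the prescriber. Sections 4.2.1, 7.3 and 8.1 have a sponsor representative abstract the patient data from the records, and the table includes drugs prescribed by other physicians. The form has no rule for a drug whose indication is unstated or dual. For Seroquel XR itself the form allows several indications to be ticked; for other drugs it has no indication field.

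Two readings of the data are at stake. One is the Section 9.3 summary itself. The other is any split between add-on and sole use. Section 2.1 describes the approval as being for add-on treatment, so readers will want that split, and it can be inferred only from whether another drug is listed. If abstractors or charting habits differ between countries, the country description, which is a stated objective in Section 1.1, is affected too.

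**Working it through.** **1. The plan's own precision figures.** The only numerical yardstick is Table 2 in Section 5. It reproduces with the simple interval p ± 1.96 × √(p(1−p)/n). For p = 11%:

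- n = 100: 1.96 × √(0.11 × 0.89/100) = 6.1 points, giving 4.9% to 17.1%, as printed.
- n = 400: 3.1 points, giving 7.9% to 14.1%, as printed.

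All 64 cells agree to rounding. Table 2 is not in dispute; it serves here to judge the size of a bias.

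**2. What is required against what is collected.**

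| Item | Limited to MDD drugs? | Name and dose? |
|---|---|---|
| Section 9.3 output at initiation | No | Both required |
| Section 9.4 output | Yes | Dose required |
| Section 4.2.2 key variables | Yes | Dose and dates |
| Appendix B concurrent-drug table | Yes | Both collected |
| Appendix B comorbidity grid | No (other conditions) | Neither collected |

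Only the first row lacks a matching source. Since Section 9.4 states the limit and Section 9.3 does not, the natural reading of Section 9.3 is the wider one.

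**3. Direction.** The indication limit can remove antidepressants from the table but cannot add any. Recorded antidepressant co-use can therefore only be too low, and an inferred monotherapy share only too high, where monotherapy means that no other antidepressant is being taken.

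**4. Size, on assumptions.** The protocol gives neither of the two inputs needed:

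- p, the true monotherapy share; assumed range 5% to 20%.
- m, the share of add-on patients for whom no concurrent drug is listed because their only antidepressant was attributed to another condition; assumed range 2% to 20%.

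Apparent share = p + (1 − p) × m. With p = 10% and m = 5%: 0.10 + 0.90 × 0.05 = 14.5%.

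| m (p = 10%) | Apparent share | Bias (points) | 95% half-width, n = 100 | 95% half-width, n = 400 |
|---|---|---|---|---|
| 2% | 11.8% | 1.8 | 6.3 | 3.2 |
| 5% | 14.5% | 4.5 | 6.9 | 3.5 |
| 10% | 19.0% | 9.0 | 7.7 | 3.8 |
| 20% | 28.0% | 18.0 | 8.8 | 4.4 |

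Over the full assumed ranges the bias runs from 1.6 points (p = 20%, m = 2%) to 19.0 points (p = 5%, m = 20%). At p = 10% and n = 400 it exceeds the half-width once m reaches 5%; at m = 2% it does not. At n = 100 it is below the half-width at m = 5% and above it at m = 10%. A larger sample narrows the interval and leaves the bias unchanged.

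**5. Between countries.** If two countries both had a true share of 10%, with m = 2% in one and m = 10% in the other, they would show 11.8% and 19.0%, an artificial gap of 7.2 points. These values are also assumed.

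**The case against.** The strongest reply is that the limit to MDD drugs is the study's scope. Section 1 speaks of regimens used to treat MDD, and Sections 4.2.2 and 9.4 and Appendix B follow it, so Section 9.3 could be read within that scope. The reading is possible, but it would then have to be written into Section 9.3; as it stands, the section promises more than the form supplies.

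Second, the form does not tell the abstractor to leave out a drug whose chart entry names another condition. Every patient has documented MDD and is under a psychiatrist's care, so an abstractor might list every antidepressant. Section 5.1 adds training, standard scripts and pilot testing. This stands: the loss is a risk that comes from an undefined term, and it is not a certainty. It also means that practice may vary between abstractors.

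Third, the grid helps identify patients who may be affected. That is true in part. It cannot tell an antidepressant from another anxiety drug, and its current-treatment column is not tied to the date of Seroquel XR initiation.

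A reader might go further and infer that such patients will be counted as on monotherapy. The protocol does not support this: Section 9 defines no such count, and the error needs a patient with no other MDD drug listed. A reader might also object that the form misses other antipsychotics, other quetiapine formulations and total exposure to the active substance. No stated output needs these: Section 9.3 promises antidepressants only.

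**Conclusion.** The mismatch is real and limited to antidepressants. Section 9.3 calls for every concomitant antidepressant with its dose, and the form reliably supplies only those that the abstractor regards as given for MDD. Names and doses not abstracted cannot be restored by the analysis, so this cannot be left to an analysis plan.

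The direction is certain: co-use too low, and any inferred monotherapy share too high. The size is unknown. The shift from 10% to 14.5% illustrates an assumed 5% loss and is not an estimate. It also takes add-on to mean any other antidepressant in use. If add-on were defined as added to a drug given for MDD, the split would be affected less, but the gap in Section 9.3 would remain. The effect on the country description is plausible and likewise unquantified; Section 9 plans description by country without statistical comparison.

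**What to change.** In the concurrent-drug table of Appendix B, change the instruction so that all antidepressants prescribed concurrently with Seroquel XR are listed regardless of indication, alongside the other MDD drugs already asked for. Add one column for charted indication with three values: MDD, other, not stated. Change Section 4.2.2 to match. Section 9.3 can then use all listed antidepressants, and Section 9.4 can keep the MDD-only view as a subset. If an add-on/monotherapy split is to be reported, define it from this list.

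The cost is one column and some extra drug lines per patient, taken from records already open at the same visit, so abstraction takes slightly longer. Sections 4.1.2 and 4.2.2 already allow the questionnaire to be revised after the pilot. If the sponsor prefers the narrower scope, the minimum is to limit the Section 9.3 wording to antidepressants for MDD. That removes the contradiction, but leaves the indication judgement undefined and the other antidepressants unrecorded.
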